In the last decade locking plates gained popularity not only for distal tibia fractures but fracture treatment in general. Recent studies raised concerns because of the inherent stiffness of these locking devices and found they might suppress fracture healing [3][4][5]. To address this issue the concept of Far Cortical Locking (FCL) was developed [6][7] and has been commercially available since 2010 in the *Zimmer MotionLoc* Screw for NCB[®] Polyaxial Locking Plate System and since 2014 in the *Zimmer MotionLoc* Screw for *Zimmer* Periarticular Locking Plate System (Zimmer Inc.).

FCL screws lock rigidly into the plate and into the far cortex, but retain a controlled motion envelope in the near cortex. The screws have an elastic shaft portion that can deflect within this motion envelope. This flexion of FCL screw shafts induces symmetric axial motion at the fracture site in response to load bearing. FCL screws are optimized to reduce the initial stiffness of a locked plating construct while retaining its construct and fixation strength. *MotionLoc* Screws for *Zimmer* Periarticular Locking Plate System reduce the locked plating construct stiffness by more than 58% while retaining construct strength [8].

Recently, a prospective observational clinical study in 31 distal femur fractures treated with *Zimmer MotionLoc* Screws for NCB Polyaxial Locking Plate System has shown a fracture healing rate of 97% (30 out of 31) after a 6 month follow up period with no implant and fixation failure.

The purpose of this observational prospective study is to systematically document the clinical outcomes of *Zimmer MotionLoc* Screws for Periarticular Locking Plate System applied in distal tibia fracture treatment and confirm safety and performance of the screws.

III. Study Objectives

The objective of this observational prospective study is to systematically document the clinical outcome of *Zimmer MotionLoc* Screws for Periarticular Locking Plate System applied in distal tibia fracture treatment and confirm safety and performance.

Primary Endpoint:

- Radiographic & clinical fracture healing at 3 months post-surgery.

Secondary Endpoints:

- Complications
- Radiologic & clinical fracture healing at 6 weeks, 3, 6, and 12 months post-surgery.
- Callus size & distribution at 6 weeks, 3, 6, and 12 months post-surgery.

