Follow-up evaluations will be performed at 6 weeks (± 14 days), 3 months (± 14 days), 6 months (± 30 days) and 12 months (± 30 days) post-surgery. Standard anteroposterior and lateral x-rays of the operated side must be obtained at each follow-up. If the treating surgeon is unable to adequately assess cortical healing due to radiographic obstruction of the implant(s), additional x-ray(s) should be performed. At 3 months a CT scan of the fracture site must be performed in addition. The “Follow-up” set of forms must be completed at each follow-up time point. This includes the assessment of radiologic fracture healing. At 6 weeks, 3, 6 and 12 months, the surgeon must assess the FIX-IT Score and document on the corresponding set of forms. At the 12

month follow-up the “Study Completion” form must be completed additionally. Copies of the original x-ray films and CT scans must be sent to the Sponsor.

Patient Withdrawal

Patient withdrawal has to be documented on the “Study Completion” form. In particular the reason for withdrawal must be documented. The occurrence of any of the following situations gives reason to withdraw a patient from the study:

- Voluntary patient withdrawal. Patients are at liberty to withdraw from the study at any time and for any reason without affecting future treatment.
- Development of a concurrent condition which would interfere with the patient's continued participation.
- Reoperation including complete removal of study device(s).
- Patient is non-compliant.

Lost to Follow-up

Patients will be considered lost to follow-up after they have missed a visit and a reasonable number of attempts to locate and evaluate them have failed. This has to be documented on the “Study Completion” form and in particular the reason should be documented. Patients lost to follow-up will not be replaced within the study.

Minimization of Subjects Lost to Follow-Up

Subject follow-up is extremely important for the conduct of a clinical study. The expectation is to maintain the highest rate of follow-up compliance possible throughout this study. No replacement is foreseen for any patient lost to follow-up. In an effort to minimize lost-to-follow-up subjects, the following recommendations and/or study requirements are essential to ensure proper patient selection and compliance:

1. Patient Eligibility: Subjects will be selected according to the inclusion/exclusion criteria detailed in Section 8 and are expected to return for all follow-up visits.

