2. Patients Counseled: Patients will be counseled during the Informed Consent process on the importance of returning for follow-up visits.
3. Patient Exclusion: Patients who are not willing to return for study required follow-up visits and/or are not willing to comply with the follow-up schedule will not be considered for enrollment into the study.
4. Subject Due Listings: In addition to proper patient selection, Zimmer Biomet will provide subject due notices to the sites on a regular basis in order to track each study participant and monitor adherence to the required follow-up visit timeframes. The subject due listings will facilitate scheduling the subjects for their return office visits.
5. Contact Tracking: Attempts to contact subjects will be documented in the study subject's medical record. It is recommended that the first three attempts be made by telephone. If

after three calls, contact has not been successful, the below is required prior to terminating the study subject from the study:

Recommended Contact Attempts

If	Then
a response is not received from 3 phone calls	the investigator should send a letter to the subject explaining the follow-up agreement per informed consent.
a response is not received from the investigator’s first letter	the investigator should send a certified letter to the subject.
a response is not received from the investigator’s certified letter	the investigator should use any additional contacts provided by the subject to contact the subject.
all attempts to contact the subject are unsuccessful or the subject is contacted and chooses to withdraw from the study	the “Study Completion” form will be completed and will specify the reason the subject is no longer participating in this study.

Radiographic Management

All radiographic imaging performed according to the protocol will be reviewed and evaluated by the investigator or qualified designee at the time of the post-operative assessment for standard patient management purposes. If a radiographic adverse event is identified by the Investigator during the course of the investigation, the Investigator must document the event and report the radiographic findings on a Complication Case Report Form for Sponsor review. It is possible that radiographs taken within this study could be used for future regulatory submissions and/or product evaluations, and may therefore require radiographic review by an unbiased independent review.

Recommended Revision Procedure

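### One missed visit followed by failed contact closes a subject out with no route back, so a subject who missed the 6-week visit could be closed before the 3-month primary assessment

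*Combined protocol and SAP*

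**What the plan says.** The rule stands in Section VI of the combined protocol and SAP, under Lost to Follow-up, and reads: "Patients will be considered lost to follow-up after they have missed a visit and a reasonable number of attempts to locate and evaluate them" are unsuccessful. The status is recorded on the Study Completion form, and lost subjects are not replaced.

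The next subsection, Minimization of Subjects Lost to Follow-Up, describes the contact effort under item 5 (Contact Tracking). The first attempts are three telephone calls. If they fail, "the below is required prior to terminating the study subject from the study". The table that follows lists a letter, then a certified letter, then any additional contacts the subject has given. Its heading is "Recommended Contact Attempts", and the rows for these steps say what the investigator should do. The last row states the consequence: the Study Completion "form will be completed and will specify the reason the subject is no longer participating in this study".

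The primary endpoint in Section III is "Radiographic & clinical fracture healing at 3 months post-surgery". That is the second scheduled follow-up visit. The first is at 6 weeks, and visits at 6 and 12 months follow.

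**The concern.** The lost-to-follow-up rule can be met at the first follow-up visit, before the primary endpoint is due. It does not require a second missed visit. It does not hold the record open until a later window has passed, and it sets no pace for the contact steps. It also does not say what happens if the subject comes back. A fracture patient who skipped the 6-week visit and did not answer may still return to the surgeon at 3, 6 or 12 months. Under the rule as written that subject has already been closed out, and the protocol gives no way to use the assessment.

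What is at stake is outcome data that could have been collected: the 3-month primary assessment, the later healing and callus assessments, and complications, which are a secondary endpoint in a study meant to confirm safety. The sample is 30 to 40 subjects without replacement, and Section VII gives no rule for a missing 3-month outcome. If the closed subjects differ from those who stay, the reported percentage is biased. The documents do not tell us in which direction.

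A second, smaller problem is that the minimum effort before closure is described in different ways, so the roughly eight sites could apply different thresholds.

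**Working it through.** **Sample size.** Section VII expects 5 patients per site in one year at 8 sites: 8 × 5 = 40, which reproduces the stated total. Section V sets a floor of 30. No dropout rate is given.

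**Timing.** The windows come from Section VI, Follow-up Procedures: ±14 days at both 6 weeks and 3 months. Six weeks is day 42. The protocol does not give 3 months in days, so day 91 is an assumption, with day 84 to day 92 as the range.

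| | 3 months = day 91 | range, day 84 to 92 |
|---|---|---|
| 6-week window closes | 42 + 14 = day 56 | day 56 |
| 3-month window opens | 91 − 14 = day 77 | day 70 to 78 |
| 3-month window closes | 91 + 14 = day 105 | day 98 to 106 |
| Gap, day 56 to opening | 77 − 56 = 21 days | 14 to 22 days |
| Gap, day 56 to closing | 105 − 56 = 49 days | 42 to 50 days |

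A site that completes the calls, letters and additional contacts within about 21 days can close the subject before the primary window opens. A site that completes them within about 49 days can close the subject before that window ends. With no intervals stated, both are allowed and neither is certain.

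**Effect of each closed subject.** If x of the n − L assessed subjects have healed and L are unassessed, the proportion among all n lies between x/n and (x + L)/n, a range of L/n. For L = 1:

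- n = 40: 1/40 = 2.5 points
- n = 30: 1/30 = 3.3 points

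As an illustration only, with assumed counts: if 4 of 40 are unassessed and 25 of 36 healed, the observed figure is 25/36 = 69.4%. The bounds are 25/40 = 62.5% and 29/40 = 72.5%. The same bounds apply to loss from any cause, so they do not measure the effect of this rule.

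**Precision.** Near 70% healing, the half-width of the exact 95% interval is 15.0 points for 28/40 and 15.9 points for 25/36. The loss of precision is small, so the concern is possible bias from subjects not assessed.

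**Contact standard, side by side.**

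| Place in Section VI | Standard |
|---|---|
| Lost to Follow-up | a reasonable number of attempts |
| Contact Tracking, sentence before the table | the listed steps are required before termination |
| Table heading | recommended |
| Table rows for letters and additional contacts | should |

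The definition turns on failure to locate and evaluate the subject, while the table turns on failure to make contact. These are not the same test.

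**The case against.** A reader might infer that one missed visit by itself ends participation. The documents do not support that. Contact must also fail, and three calls, two letters and additional contacts come first. A subject who is reached and does not choose to withdraw is not lost under this rule. Because each letter depends on no reply to the step before, the sequence could well run into or past the 3-month window.

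A reader might also infer that the rule will cost the study some 10% or more of its primary outcomes. Nothing in the documents shows this. The rule causes avoidable loss only in subjects who miss 6 weeks, fail every contact step, are closed before the 3-month assessment and would still have attended. Many people who cannot be reached by any of those routes would be missing at 3 months under any rule.

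The protocol also has safeguards: regular due notices from the sponsor, counselling at consent, exclusion of patients unwilling to return, and documented contact attempts. The analysis is descriptive, with no hypothesis test specified for the primary endpoint. The contact wording can largely be read as a general definition made operational by Contact Tracking.

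These points limit the size of the concern but do not remove it. None of the safeguards keeps a record open once contact has failed, and no section sets a pace or provides for return. The heading and rows of the table still conflict with the sentence that introduces them.

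**Conclusion.** The concern holds in a limited form. As written, the rule permits a subject who missed the 6-week visit and could not be reached to be closed out before the 3-month window opens (about day 77) or closes (about day 105), on the assumption that 3 months is day 91. Primary, secondary and complication data that could later have been obtained would then be lost.

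Each such subject leaves 2.5 points (40 subjects) or 3.3 points (30 subjects) of the primary percentage unknown. How many there would be cannot be derived from the documents. That the loss would be informative is plausible but not documented. The protocol does not expressly forbid a return; it simply provides no route for one.

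The change should be made because following the rule can discard obtainable outcomes in a small sample and the remedy is cheap. The point does not show that the study's results would be materially wrong.

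**What to change.** In Section VI, Lost to Follow-up:

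- Record a subject who misses a visit and cannot be reached as 'visit missed', and keep the subject on the due listings for all remaining visits.
- Assign lost-to-follow-up status, with its Study Completion form, only after the 12-month window (+30 days) has closed without contact.
- State that a subject who returns earlier resumes the visit schedule and is analysed.
- Leave unchanged the use of the Study Completion form for voluntary withdrawal, the other withdrawal reasons, revision and the 12-month visit.

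In Minimization of Subjects Lost to Follow-Up, reconcile the table heading and its rows with the sentence that makes the steps required. Refer to that same standard in the Lost to Follow-up definition in place of a reasonable number, so that one contact standard applies at all sites. Align the last row of the table with the new timing, so that failed contact alone no longer triggers the Study Completion form at once.

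Holding closure only until the 3-month window ends, with permission to resume, would protect the primary endpoint. Waiting until the 12-month window closes also protects the later healing, callus and complication data.

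The cost is a few sentences in the protocol, a few records kept open longer and a few more notices sent. No procedure is added.

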If a device has to be removed¹, the investigator will choose the best revision treatment method for the subject. Before revision surgery, the Investigator must document any significant radiographic findings related to the need for revision. Additionally, once the revision surgery has been completed, the Investigator must complete an Adverse Event CRF, as well as a Study Completion CRF, terminating the subject from the study.

¹Device removal after fracture healing, upon patient request or as part of standard treatment, is not considered a “Recommended Revision Procedure”.

Explanted Device Return

All components removed, except the devices removed after fracture healing upon patient request or as part of standard treatment, should be returned to Zimmer Biomet for analysis. The Investigator must notify the Clinical Study Manager prior to the return of any device. Properly prepared specimens are to be sent to:

Zimmer Biomet
Attention: Product Services Department
[name]
[name]

VII. Statistical Methods

General Statistical Methods

Considering the inclusion and exclusion criteria, per study site an enrollment of 5 patients in one year can be expected. Within one year of enrollment at 8 study sites this equals to 40 patients in total. For the purpose of this observational study this number of patients is considered to be sufficient to document first clinical outcome and assess safety and performance. Collected data will be presented descriptively. For categorical data, frequency and percentage will be calculated. For continuous data, mean, standard deviation, median, minimum and maximum will be calculated.

Comparative assessment

For comparative assessments of any non-parametric data (e.g. score between different follow-up time points) the Wilcoxon test will be used for paired, and the Mann-Whitney test for unpaired data. A significance level of $p=0.05$ will be set.

VIII. Risk Analysis

Zimmer MotionLoc Screws for the *Zimmer* Periarticular Locking Plate System have been commercially available since April 2014. The devices involved are used in accordance with the cleared indications. There are no anticipated risks specific to study participation other than the potential loss of confidentiality. There are no experimental procedures in this study and participation is not anticipated to affect the medical treatment of enrolled subjects.

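### A required device removal ends participation and the plan gives that subject no healing status, so later healing percentages tend to be overstated if completed visit forms are the denominator

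*Combined protocol and SAP*

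**What the plan says.** Five parts of the combined protocol and SAP bear on this point.

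- **Section VI, Recommended Revision Procedure.** After revision surgery for a device that had to come out, "the Investigator must complete an Adverse Event CRF, as well as a Study Completion CRF, terminating the subject from the study". Beforehand, "Before revision surgery, the Investigator must document any significant radiographic findings related to the need for revision". A footnote takes removal after healing, on patient request or as standard treatment, outside this procedure. Explanted Device Return repeats the same exemption: "All components removed, except the devices removed after fracture healing upon patient request or as part of standard treatment, should be returned".
- **Section VI, Patient Withdrawal.** "The occurrence of any of the following situations gives reason to withdraw a patient from the study"; one listed situation is a reoperation in which the study device is completely removed. On the completion form, "In particular the reason for withdrawal must be documented".
- **Section VI, Follow-up Procedures.** A set of follow-up forms is due at 6 weeks and at 3, 6 and 12 months. "This includes the assessment of radiologic fracture healing". FIX-IT is scored at the same visits.
- **Section VII, General Statistical Methods.** "Collected data will be presented descriptively. For categorical data, frequency and percentage will be calculated". No analysis set, denominator or missing-data rule follows.
- **Sections VIII and IX.** Removal or reoperation is one of the outcome categories for an adverse event. Complications, and changes in their outcome, are recorded on the Complication form while the investigation runs.

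**The concern.** A subject terminated after a required removal has no further form on which healing is due. The footnote keeps most removals of healed fractures out of this rule, so those who leave are more likely than the rest to be unhealed. Their later results are therefore missing for a reason connected with the outcome.

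Section VII does not say how such subjects enter the healing percentages. If only completed forms are counted, likely device failures leave both numerator and denominator, and the percentage tends to rise. The study has no control arm, and its aim is to document outcomes and confirm safety and performance, so its healing percentages carry much of the weight. Without a written rule the denominator is open to choice at the analysis.

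**Working it through.** **The plan's own figure.** Section VII expects 5 patients per site at 8 sites: 8 × 5 = 40, which reproduces. Section V sets a floor of 30. There is no precision or power calculation to check.

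**Inputs.** N = 40 and N = 30 come from the documents. The number *w* of unhealed subjects terminated before a visit is an assumption, as are true healing rates of 80% and 90% (later visits) and 60% (3 months).

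**Formula.** With *h* healed subjects, no other missing results and all *w* unhealed, the true rate is h/N and the rate on completed forms is h/(N − w). The ratio is N/(N − w).

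| True rate | w = 1 | w = 2 | w = 3 |
|---|---|---|---|
| 32/40 = 80.0% | 32/39 = 82.1% | 32/38 = 84.2% | 32/37 = 86.5% |
| 36/40 = 90.0% | 36/39 = 92.3% | 36/38 = 94.7% | 36/37 = 97.3% |
| 24/30 = 80.0% | 24/29 = 82.8% | 24/28 = 85.7% | not used (see below) |

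With w = 0 there is no shift. At 3 months, with one earlier removal, 24/40 = 60.0% becomes 24/39 = 61.5%, and 18/30 = 60.0% becomes 18/29 = 62.1%.

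**Plausible range for w.** The only related figure is in Section II: 31 distal femur fractures with no implant or fixation failure at 6 months. That is another bone and another plate system, and failure is not the same as removal. For 0 of 31 the one-sided 95% upper limit is 1 − 0.05^(1/31) = 9.2%, which is 3.7 subjects of 40 or 2.8 of 30. In whole subjects this allows up to 3 of 40 and up to 2 of 30. Zero is plausible, but a few removals are not excluded: at a true rate of 5%, 0 of 31 would occur with probability 0.95^31 = 0.20.

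**Direction.** Let *c* of the *w* terminated subjects be healed. The completed-forms rate (h − c)/(N − w) exceeds h/N exactly when c/w < h/N. With N = 40, h = 32 and w = 2:

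- neither healed: 32/38 = 84.2%
- one healed: 31/38 = 81.6%
- both healed: 30/38 = 78.9%

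The percentage is too high unless terminated subjects had healed at least as often as the whole group.

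**Sampling error for comparison.** The exact 95% interval for 32/40 is 64.4% to 90.9%, wider than any shift from 80.0% in the table.

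**The case against.** The strongest case on the other side has five parts.

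- **The plan does not prescribe completed forms as the denominator.** This stands. A reader might infer that the plan itself builds in an inflated rate; the text only leaves the matter open.
- **The removal is not hidden.** This stands too. It goes on an adverse event form with the reason for withdrawal, and complications are a secondary endpoint. A reader might infer that failures vanish from the report, which is wrong. A complication count does not, however, correct a healing percentage, and nothing in the text links the two.
- **The primary endpoint is hardly affected.** Largely right. It is at 3 months, and only earlier removals matter.
- **Terminated subjects need not be unhealed.** Right. A healed fracture whose device must come out for another reason, such as infection, is still terminated. This supports wording such as *tends to*, not a claim of certain bias.
- **The records may not settle healing status.** Right. Section III combines radiologic healing (three of four cortices bridged) with clinical healing by FIX-IT. The findings required before revision need include neither a cortex count nor FIX-IT. The case report forms are not in the text, so whether one of them records union cannot be seen. One cannot say that existing data settle every case.

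Denominators for other missing results, such as loss to follow-up, are also unstated. Required removal differs in that a stated rule causes the missingness and links it to likely failure.

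**Conclusion.** The concern holds in a limited form. Required removal ends follow-up, the exemption makes those who leave likely to be unhealed, and Section VII gives them neither a status nor a place in a denominator. If percentages are taken over completed forms, healing at visits after removal tends to be overstated, mainly at 6 and 12 months.

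For 40 subjects with a true rate of 80.0% and 0 to 3 unhealed removals, the excess is 0 to 6.5 points (80.0% to 86.5%). For 30 subjects with 0 to 2 such removals it is 0 to 5.7 points. These figures assume that every removed subject is unhealed and that nothing else is missing; the healing rates and removal counts are not in the documents. The shift is within sampling error and no success threshold depends on it. It is still worth fixing, because it tends in one direction and a written rule is cheap.

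**What to change.** **Section VII, a few sentences:**

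1. The analysis set is all enrolled subjects implanted with the study device.
2. A required removal before documented healing counts as not healed at later visits.
3. A subject with healing documented at a visit before removal keeps healed status.
4. For results missing for other reasons, report the observed rate with its denominator (subjects with a result, including those under rule 3, plus removals under rule 2). Add bounds over all implanted subjects, counting the missing first as all not healed and then as all healed.
5. Base the status of removed subjects on the last visit form plus the pre-revision radiographic findings. Show a sensitivity analysis in which removals with unclear union count as healed. This matters because a fracture may heal between widely spaced visits and leave no documented result.
6. State the unit of analysis, since bilateral fractures are eligible and termination for one side ends assessment of the other.

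Illustration with N = 40: 29 healed, 5 not healed, 2 removals under rule 2, 4 missing. The observed rate is 29/36 = 80.6%, with bounds 29/40 = 72.5% and 33/40 = 82.5%. If union was unclear in both removals, the sensitivity result is 31/36 = 86.1%. Completed forms alone would give 29/34 = 85.3%.

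**Section VI:** reconcile Patient Withdrawal, where complete removal gives reason to withdraw, with Recommended Revision Procedure, where termination follows when a device has to come out and a footnote sets exemptions. State whether complications are still collected to 12 months from revised subjects who still consent. The text sets no visit after termination and does not say whether the reporting duty continues.

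**Cost.** The Section VII rules need no extra patients; the price is a slightly less favourable healing rate. Continued collection under Section VI would mean a few added contacts and possibly an amendment with ethics approval.
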